### Adverse Events

*Safety of  $\omega$ 3 FFA:*  $\omega$ 3 FFAs have an excellent safety and tolerability profile. Most common side effects associated with their use in human trials include diarrhea, indigestion, nausea, fishy taste and belching. Total incidence of GI disturbances in phase 2 and 3 clinical trials has varied between 1.4 – 4.9%, with a very low rate of study termination [27]. The rate of study withdrawal

was 3.4% in a phase 3 study using EPA [20].  $\omega$ 3 FFAs have antiplatelet activity, however increased rates of bleeding have not been seen in large clinical cardiovascular trials [28].

**Risk Monitoring/Risk Reduction:**

The risk of anaphylactic reactions will be reduced by excluding any potential participants with a history of allergies to fish or shellfish. Participants will be instructed to immediately discontinue the study medication and contact the study team if they experience any signs of allergic reaction (i.e., rash, swelling, itching, cramps, wheezing, upset stomach, loose stool, nasal congestion, fainting, dizziness). If the investigators suspect that such symptoms are due to the EPA/DHA, the participant will be excluded from the study and referred to the appropriate health care provider.

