### **3.3 Primary Safety Endpoints**

$\omega$ 3 FFAs have an excellent safety and tolerability profile. Most common side effects associated with their use in human trials include diarrhea, indigestion, nausea, fishy taste and belching. Total incidence of GI disturbances in phase 2 and 3 clinical trials has varied between 1.4 – 4.9%, with a very low rate of study termination [27]. The rate of study withdrawal was 3.4% in a phase 3 study using EPA [20].

We will specifically assess the prevalence of adverse effects in subjects randomized to drug or placebo. Adverse effects which have been reported in the literature, may include:

1. Gastrointestinal adverse effects such as: abdominal pain, nausea, vomiting, diarrhea.
2. Altered (fishy) taste in the mouth. The preparation used in this trial using orange oil to mask this effect.
3. Allergic reactions.
4.  $\omega$ 3 FFAs have antiplatelet activity, however increased rates of bleeding have not been seen in large clinical cardiovascular trials [28]. We will specifically assess rates of any mucosal or skin bleeds in monthly telephone calls (1,2,3,4,5 months) and at the 6 month visit.

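### A suspected reaction to EPA/DHA removes the participant from the study, not only from study drug, and nothing in the protocol keeps that person for the month-6 assessment (minor)

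*Combined protocol and SAP*

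**What the plan says.** The rule is in Section 8, under Risk Monitoring/Risk Reduction. The paragraph opens with allergy: "The risk of anaphylactic reactions will be reduced by excluding any potential participants with a history of allergies to fish or shellfish". It continues: "Participants will be instructed to immediately discontinue the study medication and contact the study team if they experience any signs of allergic reaction". The signs are then spelled out: "rash, swelling, itching, cramps, wheezing, upset stomach, loose stool, nasal congestion, fainting, dizziness". The consequence follows: "If the investigators suspect that such symptoms are due to the EPA/DHA, the participant will be excluded from the study", with referral to a health care provider.

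Section 3.3 describes what the drug is expected to do: "Most common side effects associated with their use in human trials include diarrhea, indigestion, nausea, fishy taste and belching". Its list of adverse effects to be assessed has "Gastrointestinal adverse effects such as: abdominal pain, nausea, vomiting, diarrhea" as item 1 and allergic reactions as a separate item 3. Sections 3.3 and 8 put total GI disturbances at 1.4–4.9%, "with a very low rate of study termination", and add: "The rate of study withdrawal was 3.4% in a phase 3 study using EPA".

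Sections 4.3 and 6.2 schedule the month-6 visit for subjects in general. Neither mentions people who have been excluded or have stopped drug. Section 8.1 sets treatment follow-up at 7 days after the last dose, and Section 8.2 follows adverse events only. Section 8.4 sends withdrawn subjects to the Safety-Monitoring Panel, which looks at their data for links to adverse outcomes. That is a safety review and obtains no month-6 tissue. Section 7.1 gives no analysis population and no rule for missing data.

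**The concern.** Stopping the capsules and leaving the trial are separate decisions, and the paragraph joins them. A participant with a suspected drug reaction should stop drug. Nothing in the paragraph explains why the month-6 endoscopy should go too, and no other section restores it. The data at risk are tissue PGE2 (the Aim 1 primary outcome), the cytokine profile (Aim 2) and mucosal impedance (Aim 3). The people who lose them are selected by how they tolerated treatment.

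The exclusion can fall in either arm. Investigators judge causality while blinded (Sections 5.2 and 5.3), and the only unblinding described is for a serious adverse event (Section 8.1). The pilot exists to estimate the size and spread of response for planning a larger trial (Section 7.1), so selective loss bears on its purpose even though no power claim depends on it. The same wording could also be carried into the larger trial.

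A secondary matter is how wide the trigger is. The listed signs overlap with common effects of the drug, and the test is whether EPA/DHA is the suspected cause, not whether the symptom is allergic.

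**Working it through.** **Inputs.** 40 completers per arm (Section 3.1). Up to 90 randomized (Section 7.1), taken as 45 per arm. GI disturbance rate 1.4–4.9% and a cited withdrawal rate of 3.4% (Sections 3.3 and 8). The documents give no SD for change in PGE2, so effects are in SD units. The protocol states no power calculation, so there is no planned figure to reproduce.

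**1. Ceiling on the number excluded.** Assume every GI disturbance is attributed to drug and leads to exclusion; expected number = n × rate.
- Active arm of 40: 40 × 0.014 = 0.56; 40 × 0.049 = 1.96.
- Active arm of 45: 45 × 0.014 = 0.63; 45 × 0.049 = 2.21.
- Both arms at the same rate (assumption): 80 × 0.014 = 1.12 to 80 × 0.049 = 3.92; or 90 × 0.014 = 1.26 to 90 × 0.049 = 4.41.

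These are expected counts. At 4.9%, the binomial chance of 3 or more among 45 is 38%; at 1.4% it is 2.5%.

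**2. Overlap with people who would leave anyway.** At the cited 3.4%, 45 × 0.034 = 1.53 active participants would withdraw. With full overlap (assumption), the wording adds nothing at 1.4% and (0.049 − 0.034) × 45 = 0.68 at 4.9%. With no overlap it adds the full 0.63–2.21.

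**3. Room in the sample size.** The gap between 80 completers and 90 randomized allows a loss of 1 − 80/90 = 11.1%. If both arms lost 4.9%, 80/(1 − 0.049) = 84.1, so 85 randomized would be enough.

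**4. Precision.** 95% half-width for the arm difference, in SD = 1.96 × √(1/n₁ + 1/n₂).
- 45 and 45: 1.96 × √(2/45) = 0.413.
- Active-only loss: 1.96 × √(1/45 + 1/44.37) = 0.415, to 1.96 × √(1/45 + 1/42.795) = 0.418.
- Both arms at 4.9%: 1.96 × √(2/42.795) = 0.424.

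With t quantiles and the smaller arms, the half-width is 0.445 for 40 and 40, and 0.451 for 38 and 40, a 1.3% increase.

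**5. Shift in the estimate.** If a share f is lost and those people differ from the retained by d SD, the active-arm mean shifts by f × d. With d = 1 (assumption), this is 0.014 to 0.049 SD; with d = 0.5, the upper end is 0.025 SD. The largest is 0.049/0.413 = 12% of the half-width. The arm difference shifts by up to 0.049 SD if only the active arm loses people, and by zero if loss and d are equal in both arms.

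**6. Sensitivity.** At an assumed GI rate of 10%, 45 × 0.10 = 4.5 active participants would be affected. With d = 1 the shift is 0.10 SD, or 0.10/0.413 = 24% of the half-width.

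**The case against.** The strongest objection concerns what the paragraph is for. It opens with anaphylaxis, the pronoun in the exclusion sentence refers back to signs of allergy, and Section 3.3 treats GI effects and allergic reactions as different events. Section 5.4 has the coordinator assess the Section 3.3 effects at monthly calls, with presence and grade, and the Schedule of Events repeats adverse event evaluation through month 6. That makes most sense if people with ordinary GI effects stay in. GI intolerance appears in neither list in Section 8.4, although Section 8.4 says its listing is not comprehensive. All this stands. A reader might infer that the protocol orders exclusion for every expected GI effect; the documents do not support that. The GI part is a drafting ambiguity. The phone script named in Section 5.4 is not in the documents, so actual triage cannot be judged.

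The second objection is that retention is a matter of estimand. The aims concern changes attributable to supplementation, tissue taken months after stopping drug would dilute them, and the visit involves an endoscopy with 6 + 7 + 7 = 20 biopsies (Section 4.3). This is a fair cost, but collecting the data does not prevent an on-treatment summary, whereas data never collected cannot be summarized in any way.

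The third objection is that the numbers are too small to matter. On size this is right, and the 80-to-90 gap covers the headcount. Replacing people does not undo selection by tolerance, however. The gap in retention also exists under the allergy-only reading.

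**Conclusion.** The point holds as a minor one. The protocol states a post-randomization exclusion from the study, linked to treatment tolerance, where stopping drug would serve the safety purpose, and no section keeps the person for month 6. Loss of the month-6 data is a likely inference. A reader might go further and say the protocol cancels that visit, but the text is silent rather than explicit.

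The size is at most about 0.6–2.2 of 45 active participants if the wording is applied to every GI disturbance, and possibly only 0–0.7 more than would withdraw anyway. The worst shift is about 0.05 SD against a half-width of about 0.41 SD. These figures rest on the protocol's 1.4–4.9% rate, on every case leading to exclusion, and on an assumed 1 SD difference for those lost. A reader might also infer material bias in the arm comparison. The figures do not support that: the shift is well inside the confidence interval and cancels if both arms lose similar people. Confidence is medium, because the trigger has a benign reading.

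**What to change.** Keep the instruction to stop drug and call. Then make these changes:
- In Section 8 (Risk Monitoring/Risk Reduction), make the trigger a suspected allergic reaction to study drug, and make the consequence permanent discontinuation of study drug in place of removal from the study.
- State there that GI symptoms judged non-allergic do not end participation, and that continuing, resuming or stopping drug is left to the investigator's clinical judgement.
- In Section 6.2, add that anyone who stops drug for any reason still attends the scheduled month-6 visit, unless consent is withdrawn or endoscopy is unsafe.
- In Section 7.1, report an on-treatment summary beside the summary of all participants assessed.
- Bring the phone script into line.

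The cost is an amendment of a few sentences, with no visit added to the schedule. The downsides are a short triage call, a research endoscopy in a few people who are off drug, and reliance on clinical judgement to rule out allergy that presents with GI symptoms.

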### **8.1 Definitions**

#### **Unanticipated Problems Involving Risk to Subjects or Others (UPIRTSO)**

Any unanticipated problem or adverse event that meets the following three criteria:

- **Serious:** Serious problems or events that results in significant harm, (which may be physical, psychological, financial, social, economic, or legal) or increased risk for the subject or others (including individuals who are not research subjects). These include: (1) death; (2) life threatening adverse experience; (3) hospitalization - inpatient, new, or prolonged; (4) disability/incapacity - persistent or significant; (5) birth defect/anomaly; (6) breach of confidentiality and (7) other problems, events, or new information (i.e. publications, DSMB reports, interim findings, product labeling change) that in the opinion of the local investigator may adversely affect the rights, safety, or welfare of the subjects or others, or substantially compromise the research data, **AND**
- **Unanticipated:** (i.e. unexpected) problems or events are those that are not already described as potential risks in the protocol, consent document, not listed in the Investigator's Brochure, or not part of an underlying disease. A problem or event is "unanticipated" when it was unforeseeable at the time of its occurrence. A problem or event is "unanticipated" when it occurs at an increased frequency or at an increased severity than expected, **AND**
- **Related:** A problem or event is "related" if it is possibly related to the research procedures.

#### **Adverse Event**

An untoward or undesirable experience associated with the use of a medical product (i.e. drug, device, biologic) in a patient or research subject.

#### **Serious Adverse Event**

Adverse events are classified as serious or non-serious. Serious problems/events can be well defined and include;

- death
- life threatening adverse experience
- hospitalization
- inpatient, new, or prolonged; disability/incapacity
- persistent or significant birth defect/anomaly

and/or per protocol may be problems/events that in the opinion of the sponsor-investigator may have adversely affected the rights, safety, or welfare of the subjects or others, or substantially compromised the research data.

In case of a serious adverse event, the PI or a member of the study team will contact the research pharmacy for unblinding of the randomization code.

All adverse events that do not meet any of the criteria for serious, should be regarded as **non-serious adverse events**.

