### **5.2 Treatment Regimen**

Investigators, patients and statisticians will be blinded to drug versus placebo assignment. Patients randomized to active drug will be placed on 3 capsules a day of this preparation taken orally for six months. A matching placebo (1200 mg of ethyl oleate 3 capsules a day) will be provided to subjects randomized to placebo taken orally for six months. Both groups will take 2 capsules with breakfast and 1 capsule with their evening meal.

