### **5.3 Method for Assigning Subjects to Treatment Groups**

A randomization schedule will be generated in the Division of Biomedical Statistics and Informatics and sent to the research pharmacy. Investigators and patients will be blinded to drug versus placebo assignment and only research pharmacy personnel and statisticians will have access to the assignments until the study is completed. Medications (drug and matching placebo) will be dispensed through the Mayo research pharmacy.

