#### **5.6 Receiving, Storage, Dispensing and Return**

The research pharmacy will maintain the double-blind status of the study until all of the main outcomes have been measured. The DHA/EPA and placebo softgels will be supplied by Sancilio and Company, Inc. (Riviera Beach, FL) and stored in the Mayo Clinic Research Pharmacy at room temperature. The research pharmacy will assign participants to treatment or placebo based on a randomization table prepared by a statistician. Each participant will be instructed to swallow 2 softgels in the morning and 1 in the evening with meals (morning and evening) for a total of 3 softgels per day. The DHA/EPA softgels will each contain 1200mg of DHA/EPA for a total daily dosage of 3.6g/day. The placebo softgel will contain 1200mg of oleate. The pharmacy will maintain records of receipt, dispensation, and return pill counts for compliance.

At the completion of the study, there will be a final reconciliation of drug shipped, drug dispensed, drug returns, and drug remaining. This reconciliation will be logged on the drug reconciliation form, signed and dated. Any discrepancies noted will be documented and investigated, prior to return or destruction of unused study drug. Drug destroyed on site will be documented in the study files.

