## 8 Safety and Adverse Events

### Adverse event grading

Attribution scale. An adverse event is defined as both an expected side effect that is of a serious nature, or an unexpected side effect/event regardless of severity. All events will be graded as to their attribution (unrelated to protocol, or possibly, probably, or definitely related to protocol).

Any event that is reported to either the principal investigator or his designated research associates by the subject or medical staff caring for the subject and which meets the criteria will be documented as such.

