#### **8.3.1 Sponsor-Investigator reporting: notifying the Mayo IRB**

All adverse events will be reported to the Mayo Clinic IRB.

Serious adverse events are defined as:

- Death
- Life Threatening
- Inpatient hospitalization or prolongation of existing hospitalization
- Persistent or significant disability/incapacity

The PI will report serious adverse events to the chair of the IRB using the Serious Adverse Event (SAE) Reporting Form. The PI will sign each Serious Adverse Event form. A copy of the current consent form will be submitted with the actual risk highlighted in the current consent form. Or, if the PI recommends any changes to the consent form document, a printed and electronic revised consent form will be attached.

The IRB office will review the incoming reports and triage according to the nature of the event:

- Reports of serious adverse events that resulted in taking immediate action will be given first priority.
- Reports of serious adverse events for which the PI recommends changes to the consent form document will be given 2nd priority.
- All other reports will then be prioritized.

The members will review SAE form and supporting materials. If additional information is necessary, the IRB will contact the PI (or study coordinator if the PI is unavailable) by conference call. After review of the information, the IRB will make an initial determination of the seriousness of the event and determine what actions, if any will be required.

FDA regulations do not require non-serious adverse events (those that do not fall into the categories outlined in step 3 above) to be reported to the IRB. If non-serious adverse events are reported to the IRB, these reports will be signed by a member of the Subcommittee and returned to the investigator. The IRB will not retain a copy of these materials in the IRB office or files.

For serious adverse events that the IRB determines to be unrelated to the study drug/device/intervention, the original report and supporting materials will be kept in the IRB file. The IRB will review such reports, and if the IRB agrees with the determination that the event was unrelated to study drug/device/intervention, then a copy of the report will be returned to the PI. The IRB office will retain a list of the studies for which unrelated serious adverse events are reported. Serious but unrelated adverse event reports will not be included in the minutes of the meeting.

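### Section 8.1 sends every serious adverse event to the pharmacy for unblinding, with no condition on relatedness or need, and this conflicts with the blind promised in 4.3, 5.2, 5.3 and 5.6

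*Combined protocol and SAP*

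**What the plan says.** The unblinding rule stands under Serious Adverse Event in section 8.1: "In case of a serious adverse event, the PI or a member of the study team will contact the research pharmacy for unblinding". It is worded as something that will happen. It does not ask whether the event is related or unexpected, or whether anyone needs the assignment.

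The trigger is broad. Besides death, life-threatening events, hospitalization, disability and birth defect, the same definition adds a judgement category: "and/or per protocol may be problems/events that in the opinion of the sponsor-investigator may have adversely affected the rights, safety, or welfare of the subjects".

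Four other places describe the blind:

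- Section 5.2: "Investigators, patients and statisticians will be blinded to drug versus placebo assignment".
- Section 5.3, and section 4.3 in the same terms: "only research pharmacy personnel and statisticians will have access to the assignments until the study is completed".
- Section 5.6: "The research pharmacy will maintain the double-blind status of the study until all of the main outcomes have been measured".

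None of them mentions an exception for serious adverse events or refers to section 8.1. No other section sets out a code-break procedure.

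**The concern.** A pharmacist who receives a call under 8.1 while the subject is still on treatment cannot comply with both 8.1 and 5.6. If 8.1 is followed, an assignment is released during the trial for any serious event, including one that nobody thinks is connected with the capsules.

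What is mainly at stake is the judgement of adverse events. Section 8.3 has the sponsor-investigator evaluate each event and decide what follow-up and reporting it needs. The last sentence of 8.3.1 limits IRB reports for this protocol to SAEs and unanticipated problems that are directly related. Section 8.3.2 makes the FDA reports of individual events depend on evidence of a causal link with study drug or placebo. If the assignment is known before relatedness is judged, the judgement that decides whether the event is reported is no longer blind. Section 3.3 makes adverse effects in the two groups a safety endpoint, so that comparison is touched as well.

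Other steps for the same subject come later: the coordinator's monthly calls on presence and grade of adverse effects (4.3, 5.4), the case-by-case withdrawal review (8.4), and the month-6 endoscopy with biopsies, brushings and impedance (6.2).

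**Working it through.** The plan states no figure on this point, so there is none to reproduce. The check is a comparison of the text, followed by an illustration of size.

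**Step 1. Does the rule reach unrelated events?** Section 8.1 defines an adverse event as one associated with use of a product, which could be read as a causal filter. Two other places exclude that reading. Section 8, Adverse event grading: "All events will be graded as to their attribution (unrelated to protocol, or possibly, probably, or definitely related to protocol". Section 8.3.1: "For serious adverse events that the IRB determines to be unrelated to the study drug/device/intervention, the original report and supporting materials will be kept". An event can therefore be unrelated and still be a serious adverse event, and the 8.1 rule then applies to it.

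**Step 2. Is an exception written anywhere?**

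| Section | Who is blinded or may hold assignments | Until when | SAE exception |
|---|---|---|---|
| 4.3, 5.3 | Pharmacy and statisticians may hold them | Study completed | None stated |
| 5.2 | Investigators, patients and statisticians are blinded | Not stated | None stated |
| 5.6 | Pharmacy keeps the double blind | Main outcomes measured | None stated |
| 8.1 | PI or team contacts pharmacy for unblinding | At the SAE | Is itself the departure |

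The two time limits differ, but an SAE during treatment falls before both, because the final outcomes are measured six months after randomization (6.2). An SAE in the 7 days after the last dose may come after that subject's own month-6 sampling. It would then touch attribution but not sampling.

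**Step 3. Is attribution fixed before the code is opened?** Sections 8, 8.1, 8.2 and 8.3 contain no such requirement.

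**Step 4. Which outcomes are exposed?** PGE2 (Aim 1), qPCR (Aim 2) and sequencing (Aim 4) are laboratory measures, and a pathologist scores inflammation (3.2). Nothing says that the laboratories or the pathologist receive a code. More exposed are attribution, later adverse event grading, withdrawal decisions and, if the operator happens to know the code, choice of biopsy sites and the impedance readings (Aim 3).

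**Step 5. How many subjects?** The documents give no SAE rate. Let p be the assumed six-month risk that a subject has at least one SAE. Take n = 80 (planned completers, 3.1) and n = 90 (maximum randomized, 7.1). The expected number unblinded is n × p. The chance of at least one is 1 − (1 − p)^n.

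| Assumed p | n = 80: expected; P(at least one) | n = 90: expected; P(at least one) |
|---|---|---|
| 1% | 0.8; 0.55 | 0.9; 0.60 |
| 2% | 1.6; 0.80 | 1.8; 0.84 |
| 5% | 4.0; 0.98 | 4.5; 0.99 |
| 10% | 8.0; above 0.99 | 9.0; above 0.99 |

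Over the whole assumed range the expected number is about 1 to 9. At the lowest rate the chance that the rule is never used is still 40-45% (1 − 0.60 to 1 − 0.55).

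**The case against.** The best defence is that 5.3 and 5.6 state the general blind and 8.1 is a specific safety provision. Breaking the code for safety is a usual exception, and few SAEs are to be expected in a pilot of this size whose protocol anticipates no serious risks (3.1). That has force against calling any code break a fault. It does not answer the breadth of this one: the exception is automatic, covers unrelated events and is not acknowledged in the sections that promise the blind.

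Several stronger conclusions are tempting, and the documents do not support them:

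- A reader might infer that 8.1 hands the code to the PI or team. It says who contacts the pharmacy, not who is told. Disclosure to the caller is the natural reading, but it is an inference. Nor does 8.1 say whether one assignment or the wider code is opened.
- A reader might infer that the same people judge attribution, make the calls and perform the month-6 endoscopy. The coordinator makes the calls and the sponsor-investigator evaluates events. No operator is named for the endoscopy, and 6.2 allows some research sampling during a clinically indicated procedure elsewhere.
- A reader might take a planned, unrelated admission as the obvious example. Under the 8.1 definition of an adverse event, it is doubtful that such an admission counts as one.
- A reader might infer a definite number of avoidable code breaks. Neither the SAE rate nor the unrelated share is given.

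**Conclusion.** The conflict between 8.1 and sections 4.3, 5.2, 5.3 and 5.6 is real and can be read directly from the text. So is the absence of any requirement to record attribution before the code is opened. The consequence falls mainly on adverse event attribution and the reporting that follows from it. It falls secondarily, and only possibly, on later calls, withdrawal decisions, and biopsy and impedance sampling for the affected subjects.

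A reader might infer that the primary PGE2 result is compromised or that the trial is no longer double blind. The documents do not support that: the primary outcomes of Aims 1, 2 and 4 are laboratory measures, and the rule reaches only subjects with an SAE, provided that a single assignment is opened each time.

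The size is unknown. The range of about 1 to 9 subjects rests wholly on an assumed risk of 1-10% with no anchor in the documents. The conclusion also rests on the inference that the PI or team learns the assignment. The point deserves correction because the remedy is cheap, not because a large bias has been shown.

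One neighbouring inconsistency is separate and carries no weight here: 5.2 blinds the statisticians, while 4.3 and 5.3 give them the assignments.

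**What to change.** Reconcile 8.1 with 4.3, 5.2, 5.3 and 5.6 so that unblinding is not automatic for every SAE and the blinding sections refer to whatever exception remains. The amended text should:

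1. Require the attribution to be recorded and dated before the code is opened.
2. State who may request a code and who may receive it, and that it covers only the affected subject.
3. Where the code is needed only for regulatory reporting, send it to a named person with no role in attribution or outcome assessment. The internal board in 8.5.1 should not be assumed to fit: the documents do not show that its two members lack such roles, and its six-monthly meetings do not match the 7- and 15-day FDA deadlines in 8.3.2.
4. Log each unblinding with its date, recipient and reason, and whether attribution came first, so that the final report can give the number by arm.

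Emergency access to the code for a subject's care is for the sponsor to define. Nothing above is meant to narrow or delay it.

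The cost is a wording amendment and a log kept with the existing pharmacy records. Sample size, assays, visits and treatment are unchanged.
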